The study deploys a Type-1 effectiveness-implementation hybrid design to evaluate the effectiveness of the proposed adaptive interventions and gather data on the implementation. To evaluate the effectiveness of the interventions, the study employs a Sequential Multiple Assignment Randomized Trial (SMART) design. In the first phase, participants will be randomized into two frontline interventions for 12 weeks. Based on their outcome at the end of this phase, they will be placed or randomized into three adaptive strategies for another 12 weeks (Figure 1). The economic evaluation that addresses Aim 2, aims to weigh public health and societal costs against public health and societal benefits attributed to the interventions of different intensities with a time horizon of 12 months. To address Aim 3, we will conduct an ethnographic evaluation to identify the multi-level factors that influence the adoption and scale-up of the interventions in methadone clinics. The ethnographic evaluation is guided by the Consolidated Framework for Implementation Research (CFIR). The CFIR assesses five domains of interventions, outer settings, inner settings, provider characteristics and participant characteristics. The evaluation includes pre- and post-intervention in-depth interviews with key informants who participate in the study and ethnographic observation with participants in their daily activities at the clinics and in the community settings.

Settings

[figure not shown]
Participants are recruited from the methadone clinics in Hanoi and Ho Chi Minh City (HCMC) – the two largest urban settings in Vietnam. Criteria for selecting clinics include number of patients, estimated prevalence of methamphetamine use, availability of human resources to implement study interventions, and space for intervention activities. 10 clinics in each city will be randomly selected from those that meet the criteria.

Study schedule

The study pilot phase started in November 2020. The full study implementation phase began in May 2021. To recruit 200 HIV-positive and 400 HIV-negative methamphetamine-using methadone participants from both cities, we will screen about 5,000 patients in 20 methadone clinics. A cluster

of four methadone clinics will start every six months. We expect to complete the last cluster in October 2023.

Figure 1. Study flowchart

Participants

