- Maintenance treatment: Participants receive two daily automatic unidirectional scripted SMS reminders plus one weekly self-monitoring assessment message over 12 weeks.
- Enhanced treatment 1: Participants attend 12 weekly Matrix group counseling sessions facilitated by the clinic counselors. Our Matrix intervention has the same structure, albeit it is shorter than the original 24-sessions model.
- Enhanced treatment 2: Participants receive the same Matrix intervention plus contingency management over 12 weeks.

Definition of effectiveness measures

Effectiveness measures will be assessed at 13-, 26- and 49 weeks after the first week of frontline interventions and throughout the interventions. Primary outcomes include: (1) increase in HIV viral suppression for HIV-positive participants at 26- and 49-weeks; (2) reduction in HIV risk behaviors for both HIV-positive and HIV-negative participants at 26- and 49-weeks; and (3) reduction in methamphetamine use at 13-, 26- and 49-weeks measured by UDS (point abstinence) and self-report (continuous abstinence and longest period). Secondary outcomes include: (1) adherence to antiretroviral treatment for HIV-positive participants; 2) frequency of HIV testing for HIV-negative participants; 3) heroin use with UDS; 4) opioid overdose; and, 5) quality of life.

To acquire the primary and secondary outcomes, we will assess for the following:

- HIV viral load test. At baseline, Week 13, Week 26 and Week 49, we send blood samples of HIV-positive participants to laboratories at Bach Mai Hospital in Hanoi and HCMC University of Medicine and Pharmacy Hospital in HCMC for viral load quantification.

- Drug screening. We use an FDA-approved Multi-Drug Rapid Test Panel to detect methamphetamine, opioid, and cannabis in urine twice a week throughout the intervention period and at Week 49.
- Methadone and HIV treatment. We extract methadone and HIV treatment data from participants' medical charts. Variables of interest include length of treatment, treatment regimen, medication dose and treatment adherence.

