- Self-reported drug use. Drug use patterns (methamphetamine, tobacco and alcohol use) are evaluated based on amphetamine use behaviors, Amphetamine Cessation Symptom Assessment (ACSA), Addiction Severity Index (ASI) and Alcohol Use Disorders Identification Test-Concise (AUDIT-C) scales. ACSA, a 5-point Likert scale has been used in other studies in Vietnam. The scale includes three domains of methamphetamine withdrawal symptoms: fatigue (3 items), cravings (2 items) and anxiety (11 items). Higher scores in each domain and in total indicate greater levels of methamphetamine withdrawal symptoms. AUDIT-C is used for identifying patients who drink at hazardous levels or have active alcohol use disorders. AUDIT-C comprises 3 questions scoring on a scale of 0-12 with a cut-off point of 4 for men and of 3 for women.
- Self-reported psychosocial factors. We use the Barriers to Access to Care Evaluation (BACE) scale to assess barriers to access to mental health care (58). Participants are asked to what extend they agree or disagree with statements indicating barriers to mental health care. We use the 21-item Depression, Anxiety, Stress Scale (DASS-21) which was previously validated in Vietnam to measure mental health. The DASS-21 scale consists of 7 Likert items for each dimension (depression, anxiety and stress). For each item, respondents indicate how often it applies to them over the past week. The total score of each dimension will indicate the severity level of depression, anxiety and stress. The Medical Outcome Study: Social Support Survey scale (MOS-SSS), also validated in Vietnam, is used to measure social support. The MOS-SSS comprises 19 items covering four domains: emotional/informational support, tangible social support, positive social interaction, and affectionate support. Higher scores suggest greater support received. Quality of life is measured with the EQ-5D-5L scale which includes the EQ-5D-5L descriptive system and the EQ Visual Analogue scale (VAS). The descriptive system covers 5 dimensions (mobility, self-care, usual activities, pain/discomfort, anxiety/depression). On the EQ VAS, respondents indicate the score that represents their health status on the scale that ranges from 0 (the worst health they can image) to 100 (the best health they can image). The EQ-5D-5L was previously validated in Vietnam.

Economic evaluation

Definition of costs and data collection

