We will conduct activity-based costing for each intervention arm over the 20 methadone clinics. A template developed by UNAIDS is adapted to collect data on salaries for personnel and consultants, physical resources, clinical supplies and miscellaneous charges necessary to deliver each intervention type. Furthermore, any out-of-pocket or indirect costs to the participant will be collected at baseline, and at 13- and 26-week.

Definition of cost-effectiveness measures

Measures of cost-effectiveness analysis corresponded to the outcomes of interest in Aim 1 including (1) Substance use, (2) HIV risk behaviors among HIV-negative participants and HIV viral load, HIV adherence among HIV-positive participants and (3) Quality of life (Table 1). The cost-effectiveness analysis will measure the increment in cost between contrasted interventions divided by the increment in effectiveness measures.

Ethnographic evaluation

Pre-post intervention in-depth interviews

In each cluster, we will interview 12 key informants including methadone providers, clinic managers and participants under methadone treatment participating in the study. We will select at minimum 6 participants under treatment so that include old and young, employed and unemployed, and both responsive and non-responsive participants. All participants will receive VND 200 000 (~\$10 USD) for their time in each interview. Interviews will be audio-recorded and transcribed verbatim.

Ethnographic observation

This activity is composed of two elements. The first element involves ethnographers spending time with participants with their consent in intervention sessions and other daily activities in the clinic. Such observations will build a rich picture of interventions and intervention settings, including interactions between various groups (intervention providers, other staff, and participants). The second element involves the study master counselors to observe random intervention sessions and assess the fidelity of intervention delivery using a checklist.

Training and fidelity monitoring

In each selected clinic, a physician, two counselors and one nurse will participate in the study as intervention providers. The physician will ensure referral to HIV and psychiatric services when

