necessary; two counselors will run motivational interviewing, group education sessions and Matrix meetings; the nurse will collect urine twice a week and conduct contingency management based on the UDS results. Before the start of the intervention, to ensure the accuracy, integrity and fidelity to the EBIs, all intervention staff at methadone clinics will (1) receive didactic training on the theory behind the approach; (2) evaluate their comprehension of the concepts within and behind the approach; (3) watch a video of a Master Behavioral Counselor conducting intervention sessions and discuss the details of the session, and (4) conduct at least two pilot intervention instances. All intervention sessions, except contingency management, will be audio recorded, transcribed, and coded to ensure intervention fidelity. Intervention staff who have lower levels of intervention integrity or who have significant drift will be provided detailed feedback and supervision until there is parity with other staff.

Sample size determination

Sample sizes were chosen to compare primary outcomes based on first-stage randomization into one of two groups: high intensity or low intensity frontline interventions. Sample size calculations are conducted in PASS 2008 (65) for a two-group comparison of binary outcomes, a power of 80%, a 5% alpha level, and a conservative attrition rate of 20%. Using estimates from our prior work, we anticipate base rates of 80% to 90% for substance use and 60% to 70% for viral suppression. Based on these assumptions and a proposed sample of 200 HIV-positive participants (with 100 participants per group), we can detect randomization group differences of 20% or more for binary outcomes, such as substance use and viral load suppression. We can detect even smaller group differences for substance use outcomes in the proposed sample of 400 HIV-negative participants and the combined sample of HIV-positive and negative participants. If estimated outcome probabilities are similar between first-stage randomization groups at 12 weeks, we will pool 12-week results for even greater power in evaluating second-stage randomization differences.

Table 1. Assessment schedule

Assessments	Baseline	Week 13	Week 26	Week 49
Sociodemographic characteristics	X			X
Drug use history	X		X	X
Current drug use	X		X	X
Amphetamine use behaviors				
Amphetamine Cessation Symptom Assessment (ACSA)				

Tobacco smoking	X		X	X
Alcohol use	X		X	X
AUDIT-C				

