Barriers to access to care	X		X	X
BACE				
Mental health	X		X	X
Depression, Anxiety, Stress Scale (DASS-21)				
Social support	X		X	X
(MOS-SS)				
Quality of life	X			X
(EQ-5D-5L)				
Stigmatisation	X			X
Towards people who are under methadone treatment				
(MMT-SMS)				
Toward people who use drugs				
Toward people living with HIV				
Treatment information (from medical charts)	X	X	X	X
Methadone maintenance treatment				
HIV treatment				
Cost data	X		X	X
Opportunity costs				
Other healthcare costs				
Social costs				
Tests				
Quick and confirmatory HIV tests (not for participants with known HIV seropositivity)	X	X	X	X
Viral load test	X	X	X	X
UDS	Twice a week throughout intervention			X
Ethnographic observation	X	X	X	X
Qualitative interviews	X		X	

Data management

Different datasets collected from different sources will be linked through a unique identification code using REDCap (Research Electronic Data Capture) for quantitative data. Data will be uploaded in real-time from the 20 study clinics onto our database. The study data manager will assess transferred data for completeness, query sites regarding any inconsistencies, and code merged data files for analysis.

For qualitative data, field notes written on site are expanded and recorded electronically within 24 hours. After removing all personal identifiable information, the research team will upload password-protected transcripts on a secured database. The transcripts will be uploaded into Atlas.ti software to organize data and facilitate analysis.

Data analysis

To assess effectiveness

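### Quality of life is a secondary and cost-effectiveness outcome, but EQ-5D-5L is scheduled only at baseline and week 49, so nothing is recorded at the end of treatment (week 26)

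*Combined protocol and SAP*

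**What the plan says.** In the protocol, *Definition of effectiveness measures* opens with a visit rule: "Effectiveness measures will be assessed at 13-, 26- and 49 weeks after the first week of frontline interventions and throughout the interventions". The list of secondary outcomes in the same paragraph ends with "4) opioid overdose; and, 5) quality of life". The list of measures below it names the instrument: "Quality of life is measured with the EQ-5D-5L scale which includes the EQ-5D-5L descriptive system and the EQ Visual Analogue scale (VAS".

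*Definition of cost-effectiveness measures* carries the outcome into the economic evaluation and refers to the schedule: "HIV adherence among HIV-positive participants and (3) Quality of life (Table 1". *Study design* says that this evaluation weighs costs against benefits for "interventions of different intensities with a time horizon of 12 months".

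The columns of Table 1 are "Assessments Baseline Week 13 Week 26 Week 49". The EQ-5D-5L row reads "Quality of life X X", with the two marks under baseline and week 49. *Randomization and Interventions* places the frontline phase in weeks 1-12 and the adaptive phase in weeks 14-25.

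**The concern.** The text and the table do not give the same schedule for quality of life. If Table 1 is followed, no score is taken between baseline and a point about six months after the last intervention contact. The trial could then not show whether either stage changed quality of life while treatment was being given or when it stopped.

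The economic analysis is affected too. Intervention delivery costs arise in weeks 1-25, and the quality-of-life denominator of the ratio would be a single later value. The plan's own example, adding contingency management to Matrix for non-responders, would have no quality-of-life score at the end of the stage being costed. Scores not collected at week 26 cannot be recovered afterwards.

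**Working it through.** **Schedules side by side.** The plan states no figure for this point, so there is none to reproduce.

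| Source | Post-baseline visits |
|---|---|
| *Definition of effectiveness measures*, general rule | 13, 26, 49 |
| Same section, viral suppression and HIV risk behaviors | 26, 49 |
| Same section, methamphetamine use | 13, 26, 49 |
| Same section, quality of life | none of its own |
| Table 1, mental health (DASS-21) and social support | 26, 49 |
| Table 1, cost data | 26, 49 |
| Table 1, quality of life (EQ-5D-5L) | 49 |

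Weeks 13 and 26 are in the general rule but not in the EQ-5D-5L row. A displaced mark is unlikely: the sociodemographic and stigmatisation rows show the same baseline and week 49 pattern, and nearby rows clearly carry a week 26 mark.

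**Gap after treatment.** 49 − 25 = 24 weeks.

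**Illustration of what two visits can lose.** The documents give no EQ-5D values and no area-under-the-curve method, so the trajectories here are assumptions. Let the between-arm gain be 0 at baseline, *u* at weeks 13 and 26, and *k·u* at week 49. By the trapezoid rule, in *u*-weeks:

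- Four visits (0, 13, 26, 49): 13 × 0.5 + 13 × 1 + 23 × (1 + k)/2 = 19.5 + 11.5(1 + k)
- Two visits (0, 49): 49 × k/2 = 24.5k
- Week 26 added (0, 26, 49): 26 × 0.5 + 23 × (1 + k)/2 = 13 + 11.5(1 + k)

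| Gain kept at week 49 | Four visits | Two visits | Captured by two | Week 26 added | Captured |
|---|---|---|---|---|---|
| none (k = 0) | 31.0 | 0 | 0% | 24.5 | 79% |
| half (k = 0.5) | 36.75 | 12.25 | 33% | 30.25 | 82% |
| all (k = 1) | 42.5 | 24.5 | 58% | 36.0 | 85% |

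If the gain instead rises linearly from 0 to *u* at week 49, every schedule gives 49 × 0.5 = 24.5 and nothing is lost. Under these assumed shapes, week 26 alone recovers most of what the two-visit schedule omits.

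**The case against.** The strongest reply is that the mismatch is inferred. The visit rule is a general list and cannot mean every measure at every visit, because the next sentence limits two of the three primary outcomes to weeks 26 and 49. No section gives quality of life visits of its own, and the economic section points to Table 1 for this outcome. A reader might infer a specific promise of EQ-5D-5L at weeks 13, 26 and 49; the documents do not make one. This stands. It does not remove the point: quality of life is on the list that the rule introduces, no exception is stated, and every outcome given its own visits there includes week 26.

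Three further objections also stand:

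- Table 1 has no self-report scale at week 13, so a questionnaire there would be new.
- The effectiveness model in *Data analysis* has time points at 13, 26 and 49 weeks, but the outcomes named there do not include quality of life. One cannot say that a specified quality-of-life model has empty visits.
- The plan defines its ratio as a difference in costs over a difference in outcomes. It mentions neither QALYs nor an area under the curve, and a week 49 difference satisfies that definition.

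Because of the last objection, a large error factor cannot be claimed. A reader might assume a gain of 0.05 at weeks 13 and 26 fading to 0.01. Four visits then give (13 × 0.025 + 13 × 0.05 + 23 × 0.03)/52 = 0.0320 and two give 49 × 0.005/52 = 0.0047, which suggests a ratio overstated about sevenfold. The arithmetic is right, but both the trajectory and the estimand are brought in from outside the plan. The same gain kept to week 49 gives only 42.5/24.5, about 1.7-fold.

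**Conclusion.** The point holds in a limited form. As scheduled, quality of life has one post-baseline score, about 24 weeks after treatment ends. A transient gain is missed. It would be too strong to say that any gain during treatment is missed, because one that lasts to week 49 is observed there; only its size and timing during treatment are unknown. The economic ratio for this outcome rests on that one score.

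In area terms the share captured runs from 0% to 58% for a gain reached by week 13 and held to week 26, and is 100% for a linear rise to week 49. These figures depend on the assumed shapes and on a summary the plan does not adopt. The primary outcomes, the randomization and the sample size are unaffected. The change is still worth making, since the outcome serves two of the trial's aims and the remedy is cheap.

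**What to change.** 1. In Table 1, mark EQ-5D-5L (descriptive system and VAS) at week 26, where the other self-report scales and cost data are already marked. Week 13 is optional.
2. Reconcile the visit rule in *Definition of effectiveness measures* with Table 1 by stating the quality-of-life visits explicitly. If week 49 alone was intended, the text should say so and why.
3. Report the quality-of-life contrast at week 26 as well as week 49, and state which enters the cost-effectiveness ratio. If the 12-month effect is expressed as an area under the curve, specify that and use all available points.
4. In the same amendment, settle the participant-cost visits: *Economic evaluation* gives baseline, 13 and 26 weeks, and Table 1 gives baseline, 26 and 49. Week 26 is in both.

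**Cost:** a few more minutes at one existing interview and an amendment needing ethics approval. Participants already past week 26 would lack that score. With 20 clinics starting four at a time there are 20/4 = 5 clusters. If they started every six months from May 2021 (an assumption), two had begun by the protocol date of April 2022, and the other three could still supply week 26 in full.

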1.2. Methadone providers

Methadone providers will conduct the study interventions under the clinical supervision of the study master counselors. All methadone providers have been trained on basic addiction medicine and will receive further training to deliver the study interventions. We will conduct in-depth interviews with them before and after the intervention phase.

Randomization and Interventions

An investigator will stratify participants by HIV status and randomize them into two frontline interventions using REDCap, as shown in Figure 1. She will send the allocation results to the site research assistants who will then inform providers at the study clinics. This is an open label study so unblinding does not occur. Participants and their counselors, research assistants and data managers are aware of participants' assignment of intervention. Participants will receive two individual sessions of motivational interviewing with their counselors before they get into the frontline interventions and, in Week 13, before the adaptive strategies start. These sessions would boost participants' motivation for intervention and provide them with greater details of the upcoming intervention activities.

Two frontline interventions (Weeks 1-12)

- High intensity: Participants in this arm receive contingency management with the escalating-and-reset schedule throughout 12 weeks. This schedule means participants receive increasing rewards for consecutive negative UDS but if the streak of negative UDS is broken,

their rewards return to the starting level. The maximal reward value over 12 weeks is \$150 USD, equivalent to the average monthly income of our participants.

- Low intensity: Participants in this arm receive contingency management for the first six weeks with the maximal reward value of \$40 USD. For the last six weeks, they attend weekly group education sessions. The topics of group education include 1) Addiction mechanism, 2) Road to recovery, 3) Coping with triggers, 4) Boredom, 5) Building trust and 6) Relapse prevention.

Participants with four consecutive UDS negative with methamphetamine in weeks 11 and 12 are considered to be responsive to frontline interventions. Others are considered non-responsive. Responders to frontline interventions are placed in the maintenance treatment arm. Non-responders are randomized to either enhanced treatment 1 or 2.

Three adaptive strategies (Weeks 14-25)

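### Three unranked primary outcomes share one 5% alpha with no deciding contrast, week, success rule or multiplicity rule; if any one success counts, the false positive chance is about 11-14% (one test per outcome) or 13-23% (one per measure)

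*Combined protocol and SAP*

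**What the plan says.** All references are to the combined protocol and SAP.

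- **Definition of effectiveness measures.** Three primary outcomes are numbered but not ranked. The first is given as "Primary outcomes include: (1) increase in HIV viral suppression for HIV-positive participants at 26- and 49-weeks". The second is HIV risk behaviors in all participants, also at Weeks 26 and 49. The third is "reduction in methamphetamine use at 13-, 26- and 49-weeks measured by UDS (point abstinence) and self-report", where self-report covers two measures: continuous abstinence and longest period. The Abstract lists the same three, also without an order.
- **Sample size determination.** The contrast used for sizing is clear: "Sample sizes were chosen to compare primary outcomes based on first-stage randomization into one of two groups", high or low intensity. The error settings are "a power of 80%, a 5% alpha level, and a conservative attrition rate of 20" per cent. With 100 HIV-positive participants per group, the section says "we can detect randomization group differences of 20% or more for binary outcomes".
- **Data analysis, To assess effectiveness.** One longitudinal mixed model is planned, unadjusted and adjusted. It has first-stage and second-stage indicators, time, indicator-by-time terms and a stage-by-stage interaction. The section does not say which term, combination of terms, week or model version decides a primary outcome. HIV risk behaviors are not mentioned there.
- **Analysis of non-adherence and missing data; Interim analyses.** Analysis is by intention to treat and no interim analysis is planned, so no alpha is spent on interim looks. Neither section gives a success rule, a testing order or a multiplicity rule.

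**The concern.** A single 5% level protects a single test. Here there are three outcomes and five measures, each readable at more than one week and from more than one model term, and no rule links them. If a nominally significant result on any one outcome were presented as the trial succeeding, the chance of a false claim would exceed the stated 5%.

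The frontline contrast used for sizing does not settle this. In a model with indicator-by-time terms, high versus low can be read at Week 13, 26 or 49, or as a joint test. At Weeks 26 and 49 there is a further difficulty. Because the model also contains second-stage indicators and a stage-by-stage interaction, a first-stage coefficient is conditional on second-stage treatment. Under Randomization and Interventions, only frontline responders are placed in the maintenance arm, so second-stage treatment is partly a result of the frontline arm. No single coefficient in the model compares the two frontline assignments as randomized at those weeks.

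The study is open label and the data managers know the assignments. A deciding measure, week or contrast chosen after data accrue would therefore be hard to defend.

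**Working it through.** **1. The plan's own figure.** Inputs from Sample size determination: 100 HIV-positive participants per group, 20% attrition, 80% power, 5% alpha (two-sided assumed), viral suppression base rate 60-70%. Completers: 100 × 0.8 = 80 per group.

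Power = Φ[(|p1−p2|√n − z√(2p̄(1−p̄))) / √(p1(1−p1)+p2(1−p2))], pooled variance, no continuity correction.

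- 60% v 80%, n = 80: (0.2×8.944 − 1.96×0.648)/0.632 = 0.82, so power is 79.4%. The required n is 82, or 103 after attrition.
- 70% v 90%, n = 80: power 89.3%. The required n is 62, or 78 after attrition.

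The stated 100 per group for 20 points reproduces for one test at 5%.

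**2. False positive chance if any one success counts.** With k independent tests at 5% the chance is 1 − 0.95^k.

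- k = 3 (one per outcome): 1 − 0.95³ = 14.3%.
- k = 5 (one per measure: 1 + 1 + 3): 1 − 0.95⁵ = 22.6%.

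Correlation lowers these figures. The documents give none, so a common outcome correlation r from 0 to 0.9 is assumed. Viral suppression is tested only in the 200 HIV-positive participants out of 600. If the other outcomes use all 600, its test statistic correlates with theirs at r × √(200/600) = 0.58r. Multivariate normal simulation (2,000,000 draws, each test two-sided at 5%) gives:

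| r (assumed) | 3 tests | 5 tests |
|---|---|---|
| 0 | 14.3% | 22.6% |
| 0.5 | 13.3% | 19.3% |
| 0.8 | 11.7% | 14.9% |
| 0.9 | 10.8% | 12.8% |

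**3. Power under a rule that holds 5% across the three outcomes.** Assumptions: independent tests, 20% attrition, no clinic effect. Viral suppression is 60% v 80% with 80 per group. Urine drug screening (UDS) is 80% v 60% with 600/2 × 0.8 = 240 per group. Power for each test alone, by alpha:

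| Test | 5% | 2.5% | 1.67% |
|---|---|---|---|
| Viral suppression | 79.4% | 70.3% | 64.6% |
| UDS, 20 points | 99.8% | 99.5% | 99.3% |

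Holm, by exact enumeration over three tests:

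- Risk behaviors null: viral suppression 70.4%, UDS 99.5%.
- Risk behaviors at an assumed 80% power: viral suppression 76.7%, UDS 99.6%.

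Fixed sequence, UDS first, power for viral suppression:

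- Tested second: 0.998 × 0.794 = 79%.
- Tested third, risk behaviors at 80% power: 0.998 × 0.80 × 0.794 = 63%.
- Tested third, risk behaviors null: 0.998 × 0.05 × 0.794 = 4%.

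If all three must succeed, no adjustment is needed, but overall power is 0.998 × 0.794 × 0.80 = 63%.

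**4. Sensitivity to a smaller UDS effect.** If the UDS effect were 12 points (80% v 68%, an assumption), UDS alone has 85.2% power. Holm then gives UDS 76% and viral suppression 69% with risk behaviors null, or 81% and 75% with risk behaviors at 80% power.

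**The case against.** The strongest reply is that the inflation is conditional. The plan never says that one success is enough. The outcomes address different questions, one of them in a different population, and three separately reported claims need no adjustment. That is right, and it limits the finding: the percentages describe one possible reading of a silent plan. It does not remove the finding, because the plan does not state the separate-claims reading or the all-must-succeed reading either.

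A reader might go further and count every measure at every listed week: 2 + 2 + 3×3 = 13 tests, or 1 − 0.95¹³ = 49% if independent. The documents do not support this. They plan a longitudinal model and nowhere state separate tests at each week.

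A reader might also infer that the sample size is wrong. It is not on this ground, since it reproduces for a single test at 5%.

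In the other direction, applying a correlation of 0.9 to every pair of tests would give 8.4% and 10.2%. That is too lenient, because viral suppression is tested in only a third of the sample.

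Two further objections stand in part. A 20-point UDS effect with 240 per group makes adjustment look almost free for UDS; the protocol itself expects to detect smaller differences in the combined sample, hence the 12-point sensitivity. Calling the self-report measures supportive changes their declared status as primary, so that is a decision for the sponsor to make openly.

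**Conclusion.** The point holds. The plan has three unranked primary outcomes, one 5% alpha, and no deciding contrast or week, success rule or multiplicity rule. HIV risk behaviors are also missing from the outcomes named in the effectiveness analysis.

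If any one success counts, the false positive chance for the frontline contrast is roughly two to three times the stated level with one test per outcome, and up to about four and a half times with one per measure. The upper ends need only the 5% level, the count of tests and independence. The lower ends rest on an assumed outcome correlation of 0.9 and on the other outcomes using all 600 participants. The documents do not show that the sponsor intends the any-one-success reading; they fail to exclude it. This should be settled before analysis.

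**What to change.** Before analysis, amend the plan as follows.

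1. For each primary outcome, name one measure, one week and one high versus low frontline contrast. Include HIV risk behaviors, with the measure defined.
2. If the week is 26 or 49, estimate the contrast by first-stage assignment, averaged over the second-stage treatment that follows. Use a combined contrast or a model without second-stage terms, not a single first-stage coefficient conditional on second-stage treatment.
3. State the success rule. If any one success counts, apply Holm across the three outcomes at 5%, or a fixed sequence whose order is set in advance.
4. Label the remaining weeks and measures as supportive. Keep the second-stage comparison as a separate, labelled question.
5. State the resulting power for the rule chosen.

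**Cost.** The section on communicating protocol amendments requires scientific advisory committee advice and ethics review. No participants or visits are added. Holm costs viral suppression between about 3 and 9 points of power and leaves UDS above 99% for a 20-point effect. A fixed sequence with UDS first costs viral suppression almost nothing if it is second. If HIV risk behaviors come before it, the cost is large, and viral suppression is all but lost if risk behaviors show no effect. The order therefore needs to be chosen with all three outcomes in view.
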